Subjects will be screened to assure they meet all of the inclusion criteria and none of the exclusion criteria. All eligible subjects will be required to give informed consent. A complete history, full physical examination, full neurologic examination, vital signs, laboratory screening (including urine pregnancy test for women of childbearing potential), urine drug screen, IQ screen with Peabody Picture Vocabulary Test, full cognitive battery (see below), and lifetime assessment of suicidal ideation/behavior measured by the Columbia-Suicide Severity Rating Scale (C-SSRS) will be obtained.

Visit 2 Baseline/Randomization (Study week 0)

At this visit all subjects who had successfully completed all screening tests and had no significant abnormalities on baseline laboratory, physical exam, neurologic exam, or IQ testing will be randomized to study drug. At this visit, neuropsychological testing will be conducted before the first dose of study drug is administered. Subjects will be randomized and study drug will be dispensed.

Visit 3 Home testing (Study week 1)

At this visit, a partial neuropsychological assessment of cognitive function and behavioral testing will be performed. The assessments at this visit consist of online CNS-Vital Signs computerized cognitive tests and behavioral questionnaires (Profiles of Mood States

(POMS), Adverse Events Profile (AEP), & cognitive/behavioral subsets of QOLIE-89). Partial neuropsychological assessment will be conducted. Telephone contact will be made to check on adverse events and to encourage compliance.

Visit 4 Home testing (Study week 2)

At this visit, a partial neuropsychological assessment of cognitive function and behavioral testing will be performed. The assessments at this visit consist of online CNS-Vital Signs computerized cognitive tests and behavioral questionnaires (Profiles of Mood States (POMS), AEP, & cognitive/behavioral subsets of QOLIE-89). Partial neuropsychological assessment will be conducted. Telephone contact will be made to check on adverse events and to encourage compliance.

Visit 5 Clinic testing (Study week 3)

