At this visit, a brief physical examination, brief neurologic examination, vital signs, full neuropsychological assessment of cognitive function and behavioral testing will be performed. Full neuropsychological assessment will be conducted and perampanel blood levels will be collected. Time of last dose will be collected, suicidal ideation/behavior since last visit (C-SSRS) will be obtained, and adverse events will be assessed.

Visit 6 Home testing (Study week 4)

At this visit, a partial neuropsychological assessment of cognitive function and behavioral testing will be performed. The assessments at this visit consist of online CNS-Vital Signs computerized cognitive tests and behavioral questionnaires (Profiles of Mood States (POMS), AEP, & cognitive/behavioral subsets of QOLIE-89). Partial neuropsychological assessment will be conducted. Telephone contact will be made to check on adverse events and to encourage compliance.

Visit 7 Home testing (Study week 5)

At this visit, a partial neuropsychological assessment of cognitive function and behavioral testing will be performed. The assessments at this visit consist of online CNS-Vital Signs computerized cognitive tests and behavioral questionnaires (Profiles of Mood States (POMS), AEP, & cognitive/behavioral subsets of QOLIE-89). Partial neuropsychological assessment will be conducted. Telephone contact will be made to check on adverse events and to encourage compliance.

Visit 8 Clinic testing (Study week 6)

At this visit, a full physical examination, full neurologic examination, vital signs, laboratory screening (including urine pregnancy test for women of childbearing potential), urine drug screen, full neuropsychological assessment of cognitive function and behavioral

testing will be performed. Full neuropsychological assessment will be conducted and perampanel blood levels will be collected. Time of last dose will be collected, suicidal ideation/behavior since last visit (C-SSRS) will be obtained, and adverse events will be assessed.

F. Subject Reimbursement Rates

Subject Reimbursement Rates (total \$1300):

Event	1	2	3	4	5	6	7	8
Week	Screen	BL	1	2	3	4	5	6
Clinic vs Web	Clinic	Clinic	Web	Web	Clinic	Web	Web	Clinic
Payment	\$100	\$100	\$200	\$100	\$200	\$100	\$100	\$400

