A complete physical examination will consist of determinations of sitting blood pressure, weight, heart rate, assessment of physical condition (general appearance, skin and skin structure, HEENT, abdomen, cardiovascular, respiratory, musculoskeletal, genitourinary and central nervous systems). Brief physical examinations will consist of determinations of sitting blood pressure, weight, heart rate, and an assessment of physical condition, as required to determine change from the previous visit, and an assessment of adverse effects focused on skin and neurological systems.

2. Laboratory assessments (Study weeks -1 and 6)

A. Blood and Urine Samples

Blood work assessments will be obtained at visits 1 & 8.

The hematology parameters to be determined are: RBC count, hemoglobin, hematocrit, WBC count, platelet count, cell morphology and complete WBC differential count (neutrophils, bands, lymphocytes, monocytes, eosinophils and basophils).

The chemistry parameters to be determined are: SGOT, SGPT, alkaline phosphatase, albumin, total protein, total bilirubin, sodium, potassium, chloride, calcium, phosphorous, creatinine, blood urea nitrogen, uric acid and glucose. The total chemistry panel will be obtained at visits 1 & 8.

Urine Pregnancy tests will be performed on women of childbearing potential at study weeks -1, and 6 (visits 1 & 8).

Blinded PER blood levels will be collected at study weeks 3 and 6 (i.e., visits 5 & 8). PER levels will be sent to an outside contract lab. PER levels may be sent to the hospital laboratory for immediate analysis if testing is available. Results are to be reviewed and stored by a non-blinded investigator.

C. Adverse Event Procedures

An ADVERSE EVENT (AE) is a noxious and unintended event observed in, or reported by, a subject who is participating in (or has participated in) a clinical study and/or has received study medication. The AE may be related temporarily either to immediate or long-term use of the drug; the AE may not necessarily be caused by the drug. Overdose is regarded as an adverse event. Any event meeting these criteria is to be considered an adverse event, regardless of whether or not it is considered drug related.

All adverse events will be reported on the appropriate Case Report Form; details should include the type of event, date of onset, duration, intensity, causality relationship to the study drug(s), and outcome. Wherever possible, a diagnosis rather than symptom(s) should be reported.

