 - d. Consent is withdrawn. Subjects will be encouraged to complete the study, although they may withdraw at any time without prejudice.
4. Subject replacement.

Subjects who are dropped from the study prior to completion of all cognitive testing will not be replaced.

Subjects who are withdrawn prior to completion of at least one set of cognitive testing on treatment drug (i.e., prior to visit 5/study week 3) may be replaced.

5. Follow-up of discontinued patients

Subjects who receive study drug and are discontinued from the study will have all safety assessments completed, including a complete physical examination and laboratory evaluation including chemistry, hematology with differential, urinalysis and urine pregnancy test as required at study termination. This testing should be done as soon as possible. Medical follow-up of any severe adverse events or clinically significant abnormal laboratory values will continue until the abnormality resolves, and adequate medical explanation is apparent. Such data will be provided to Eisai.

X. STATISTICAL EVALUATION

A. Sample Size

We assume that the 4 groups (3 PER treatments and a placebo group) are equally spaced (in terms of z-score) at the time point of maximum drug effects (end week 1 for 4mg group and end week 3 for titration to 2mg x2wks then 4mg group), with a maximum difference of 0.24 (which is the difference between the placebo group and treatment at max effect). We then assume that over the 4 visits after max drug effect the z-scores get closer together until

they are equal at the treatment week 6th. The calculation indicates that at least 18 subjects are needed in each group to have 80% power. Since there are 4 groups, the total sample at least finishing assessment at end of week 6 (event 8) would be $19 \times 4 = 76$. Enrollment will include 20% (n=15) more to account for dropouts prior to assessment at end of visit 2 (baseline), and ~15% (n=12) more for dropouts before end of event 8 (treatment week 6). Thus, the total enrollment sample will be 103 subjects.

In summary, the 4 total groups (3 PER treatment, 1 placebo) would need at least 19 subjects per group (76 total), and total enrollment would be rounded to 105 to account for dropouts.

B. Methodology for statistical analysis

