This method with a similar overall score has been employed in prior investigations. This approach avoids potential Type I errors from multiple statistical comparisons and Type II errors resulting from reduced statistical sensitivity as a result of correcting for multiple comparisons. Analyses of individual components of the computer and neuropsychological assessment are secondary endpoints meant to evaluate sensitivity of the primary endpoint and examine the pattern of neuropsychological effects. All other endpoints are supportive and are safety assessments. Hence no adjustments for multiplicity are planned. P-values for these safety variables are not meant to show superiority and thus testing each of these variables at the $p=0.05$ level without multiplicity adjustment is a more conservative approach, which is appropriate for safety assessments and for secondary analyses of the pattern of impairments. The importance of the results should be evaluated in terms of actual differences and the risk/benefits offered by the drug to the patients.

The secondary outcome variables will be:

1. Compare titration rates for changes from Baseline (visit 2) to the end of titration (study week 3) and end of maintenance (study week 6) using Z-scores from full neuropsychological battery. The outcome variable for this analysis will be an overall neuropsychological composite Z-score, calculated by averaging individual z-scores of the selected performance measures from the computerized cognitive test battery (i.e., z-scores for the domain scores for executive function and processing speed), the average for individual Z-scores for AEP, POMS, QOLIE-cognitive questions (average of 3 scores), and the noncomputerized cognitive scores (i.e., average of z-scores for MCG immediate, MCG delayed, SDMT, Stroop-average score).
2. Compare titration rates for TEAEs and dropouts due to TEAEs across visits 3-8 (i.e., weeks 1-6).
3. Separate comparisons of titration rates for behavioral overall scores and cognitive overall scores.
4. Comparisons of titration rates and habituation over time for individual measures.

Summary statistics will be calculated by treatment for each evaluation of antiepileptic blood levels (ABLs). Additional analyses of data will be performed which take the ABLs into account. Linear correlations of plasma concentrations and the overall composite and individual score variables will be plotted with a fitted regression line superimposed for each condition.

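### Adverse events are sought by telephone in the fastest arm's assumed peak week but in clinic with examination in the slowest arm's, which may hide a TEAE excess with fast titration

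*Combined protocol and SAP*

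**What the plan says.** Section X.B, secondary outcome 2, is to "Compare titration rates for TEAEs and dropouts due to TEAEs across visits 3-8 (i.e., weeks 1-6". Adverse events are also to be tabulated by treatment and study period, a term that the plan does not define.

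The way events are sought depends on the week (Section VI.E). For the home visits at weeks 1, 2, 4 and 5: "Telephone contact will be made to check on adverse events and to encourage compliance". No examination takes place in those weeks. For week 3: "At this visit, a brief physical examination, brief neurologic examination, vital signs, full neuropsychological assessment". Section IX.B.1 adds that the brief examination includes "an assessment of adverse effects focused on skin and neurological systems". For week 6: "At this visit, a full physical examination, full neurologic examination, vital signs, laboratory screening". At both clinic visits, "suicidal ideation/behavior since last visit (C-SSRS) will be obtained, and adverse events will be assessed". All four arms follow this schedule, and subjects and staff in direct contact with them are blinded.

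Section X.A assumes that maximum drug effect falls at "end week 1 for 4mg group and end week 3 for titration to 2mg x2wks then 4mg group". It names no peak week for PER-1 (2 mg for one week, then 4 mg).

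Three other provisions bear on the point. The 19-item Adverse Events Profile (AEP) is completed every week, at home as well as in clinic (Section VI.C and Appendix A). The case report form records each event's onset date and duration (Section IX.C). Subjects who stop after receiving drug have a complete physical examination (Section IX.E).

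**The concern.** A common schedule in blinded arms normally makes event detection comparable between arms. Here the treatment factor is the timing of exposure, so the arms peak in different weeks and the shared schedule does not give them the same detection method at peak. On the plan's own assumption, PER-3 peaks in a telephone week and PER-2 in a clinic week with an examination aimed partly at adverse effects.

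Some of the drug's known effects listed in Section IX.C, such as poor coordination, abnormal gait and weight gain, can be found by an examiner in a subject who does not mention them. If such events are found less often by telephone, fast titration looks better relative to slow titration than it is. That is the unfavourable direction for a safety comparison. Study question 1 asks about side effects at different titration rates, and Section X.B says that results should be judged by the actual differences. Those differences are what a detection imbalance would shift.

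**Working it through.** **Plan's own figure.** The plan gives no expected TEAE rate, difference or power, so there is nothing to reproduce. The sample size in X.A concerns the composite z-score and does not enter the detection model.

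**Step 1: detection mode at the assumed peak.**

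| Arm | Assumed peak | Source | Mode |
|---|---|---|---|
| PER-3 | week 1 | X.A | telephone |
| PER-1 | week 2 | inferred from first week on 4 mg (VI.C) | telephone |
| PER-2 | week 3 | X.A | clinic with examination |

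**Step 2: model for weeks 1-6 incidence when true risks are equal.** All inputs are assumptions; the documents give none of them.
- P: true event probability in the peak week, the same in each active arm, 0.3 to 0.5
- b = 0.05: event probability in each other week
- s: telephone sensitivity relative to a clinic visit, 0.6 to 0.9
- r: share of telephone-missed events recorded at the next clinic visit, 0 to 0.8

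Effective detection in a telephone week is d = s + (1 - s)r. In a clinic week it is 1. There are four telephone weeks and two clinic weeks.

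PER-3, peak in a telephone week: observed incidence = 1 - (1 - Pd)(1 - bd)^3 (1 - b)^2

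PER-2, peak in a clinic week: observed incidence = 1 - (1 - bd)^4 (1 - P)(1 - b)

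Example with P = 0.5, s = 0.6, r = 0, so d = 0.6:
- PER-3: 1 - 0.70 × 0.97^3 × 0.95^2 = 42.3%
- PER-2: 1 - 0.97^4 × 0.50 × 0.95 = 57.9%

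| P | s | r | d | PER-3 | PER-2 | Spurious PER-2 excess |
|---|---|---|---|---|---|---|
| 0.5 | 0.60 | 0 | 0.600 | 42.3% | 57.9% | 15.6 points |
| 0.5 | 0.75 | 0 | 0.750 | 49.7% | 59.2% | 9.5 |
| 0.5 | 0.75 | 0.5 | 0.875 | 55.6% | 60.3% | 4.7 |
| 0.3 | 0.75 | 0.5 | 0.875 | 41.8% | 44.4% | 2.6 |
| 0.5 | 0.90 | 0.5 | 0.950 | 59.1% | 60.9% | 1.8 |
| 0.3 | 0.90 | 0.8 | 0.980 | 45.2% | 45.6% | 0.4 |
| 0.5 | 1.00 | any | 1.000 | 61.3% | 61.3% | 0.0 |

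**Step 3: a real excess with fast titration.** Take true peak-week risks of 50% (PER-3) and 30% (PER-2). The observed peak-week difference is 0.5d - 0.3. The true 20 points appear as 0 (d = 0.6), 7.5 (d = 0.75), 13.8 (d = 0.875) or 17.5 (d = 0.95).

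**Step 4: power for that difference with full detection.** With 76/4 = 19 per arm and a two-sided 5% level (sidedness is my assumption), power = Φ{[0.20√19 - 1.96√(2 × 0.4 × 0.6)] / √(0.5 × 0.5 + 0.3 × 0.7)} = Φ(-0.72), or about 24%. The significance test is weak whatever the detection mode. The estimated difference is what a reader would use.

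**Step 5: titration against maintenance.** The only stated boundary is in secondary outcome 1, which closes titration at week 3 and maintenance at week 6. Weeks 1-3 hold two telephone contacts and one clinic contact, and so do weeks 4-6. With a constant weekly event rate and no later recovery, the expected ratio between periods is (2s + 1)/(2s + 1) = 1.00 for every s. If titration ended in each arm with its first week on 4 mg, the clinic share in titration versus maintenance would be 0/1 v 2/5 (PER-3), 0/2 v 2/4 (PER-1) and 1/3 v 1/3 (PER-2). The plan does not define periods that way.

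**The case against.** The strongest reply is that lower telephone sensitivity is assumed, and that much of the plan works against a large effect.

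- **Symptoms.** Dizziness, sleepiness, tiredness, irritability, nausea and headache are matters that a caller can elicit. This stands, and it argues for the upper end of the sensitivity range.
- **The AEP.** A reader might infer that home weeks rest on a telephone call alone. They do not: the AEP asks about adverse effects in all six weeks and every arm, and it is analysed in the subjective composite and as an individual measure. But no rule carries its answers into the TEAE listing, so it does not repair secondary outcome 2.
- **Persistence and onset dates.** X.A has the groups converging until week 6. If PER-3's effect declined in a straight line from week 1 (my assumption), (6 - 3)/(6 - 1) = 60% would remain at the week 3 examination, and an event found then can be dated back. This supports substantial recovery, though not of events that have resolved and been forgotten. X.A's peak also concerns z-scores, so applying it to TEAEs is an extrapolation.
- **Dropouts.** Withdrawal for a TEAE depends little on visit mode, and those who stop after receiving drug are examined. This part of secondary outcome 2 is hardly touched.
- **Standing of the outcome.** It is supportive and not meant to show superiority. This stands, and it limits the severity.

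A reader might also infer that the schedule inflates maintenance rates relative to titration rates. Step 5 shows that it does not on the stated boundary. Separating titration from maintenance TEAEs appears in the background rationale and is not a listed outcome. Nor is detection at its strongest at PER-2's peak: week 6, with full examinations and laboratory tests, is the most intensive visit. A peak in a telephone week for both faster arms rests on an inference for PER-1.

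**Conclusion.** The concern holds in a limited form. The mode of ascertainment differs between PER-3's and PER-2's assumed peak weeks, and neither blinding nor the shared schedule removes that. If telephone contact is less sensitive, the PER-3 versus PER-2 comparison of TEAE incidence is biased towards hiding an excess with fast titration. The spurious PER-2 excess is about 0.4 to 15.6 points over the assumed ranges, and zero if the two modes detect equally well. The documents do not show which applies, and the plan collects nothing that would tell. They do not support saying that the bias is present, that it is large, or that it reaches TEAE dropouts or a titration-versus-maintenance contrast at week 3. Severity is minor.

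**What to change.** 1. Ask the same scripted adverse-event questions at all six on-treatment contacts, and complete them before any examination at weeks 3 and 6.
2. Add a source field to the adverse-event form: subject report, or examination, vital signs, weight or laboratory.
3. Assign events to weeks by onset date.
4. Report secondary outcome 2 for all TEAEs and also for subject-reported TEAEs alone, with examination-only and laboratory-only findings tabulated separately. Keeping the all-event comparison means that no safety finding is removed.
5. Define study period for the adverse-event table in Section X.B.

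The cost is one form field, a short script and an extra table. Some difference between telephone and in-person questioning will remain, so the subject-reported comparison reduces the imbalance without removing it.
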